#### Administrative information

Title	Agreement of antigen tests on oral pharyngeal swabs or less invasive testing with RT-PCR, for detecting SARS-CoV-2 in adults: A prospective nationwide observational study
Trial registration	www.clinicaltrials.gov
Protocol version	May 19th, 2021; v2.4
Funding	
 
Companies providing antigen tests, hereafter termed the providers.
 
The provider delivers 800 antigen-tests free-of-charge.
 
The provider will pay a divided share of the cost of performing the additional testing of individuals suspected or diagnosed with SARS-CoV-2 and the RT-PCR retesting of previously positive individuals.
 
The provider will pay a divided share of the costs of the administrative, analytical work and open access publishing.
 
All funds are collected at a trust account administrated by Hvidovre Hospital, Region Hovedstaden and cost for regional testing is covered from this account. Any excess funds will be divided between the providers when the study is published.
 
The planned RT-PCR testing for SARS-CoV-2 of individuals with suspected COVID-19
 

	infection is conducted as planned by the Danish health-care system
Roles and responsibilities	The study will be open as a national project welcoming all Departments of Clinical Microbiology (DCM) in Denmark, all test centers and all medical companies that wishes to promote antigen tests in Denmark.
	The steering group will: write and publish the protocol, assess which tests that have the documented quality to be included in the study, oversee the execution of the study, data analysis and drafting of manuscript.
	The steering group consists of [name], consultant, MD, PhD, DCM Hvidovre Hospital, [name], Chief consultant, MD, PhD, DCM Hvidovre Hospital, [name], professor, MD, MPH, PhD, Department of Infectious Diseases Rigshospitalet, [name], laboratory head, MSc, PhD, DCM Rigshospitalet, and [name], head of department, MD, Dr.M.Sci., DCM Rigshospitalet. [name] will draft the protocol with input from the other authors.
	The steering group will establish a writing group consisting of individuals actively contributing to the study.
	Providers participating the study will be entered into the protocol and be known to the public.  The providers will have access to view data and manuscript 10 days prior to publishing but will not have any influence on the preparation or publication of the manuscript.

#### Introduction

# Background and rationale

Multiple antigen tests targeting SARS-CoV-2 are being marketed commercially, accompanied by reporting of accuracy by the vendor. To evaluate the real-life accuracy of such tests, independent user-initiated studies are needed. Antigen tests are interesting from a public health perspective, as they are rapid (approximately 15-20 minutes) compared to centralized amplification based testing e.g. RT-PCR, but previous antigen tests e.g. for Influenza and Respiratory Syncytial Virus have shown unacceptable low sensitivity when compared to nucleic acid based testing (NAT, e.g. RT-PCR) (Chartrand 2012, Bruning 2017, Merckx 2017). CE marked antigen tests are mostly validated for use with nasopharyngeal swabs. Unfortunately, nasopharyngeal swabbing is normally avoided in adults due to the discomfort for the patient leading to risk of non-compliance and are widely substituted by oropharyngeal swabbing. In the present protocol oropharyngeal

	swabs or less invasive testing e.g. nasal swabs will be used to limit the discomfort for the participating individuals and to reflect the real-life testing approach in adults. An alternative test strategy with saliva swabs with RT-PCR testing will be included as part of the study.
Objectives	To evaluate the analytical and clinical sensitivity and specificity of antigen tests performed as oropharyngeal swabs, outer nasal swabs, saliva swabs, self-test or breath tests for SARS-CoV-2 towards standard RT-PCR testing
Trial design	Prospective accuracy observational study combined with retrospective analytical sensitivity and specificity study.

# Methods: Participants, interventions, and outcomes

- · · · · · ·	
Study setting	Test centers screening out-patients and hospital staff for SARS-CoV-2 and
	hospitalized patients positive for SARS-CoV-2. Test centers are invited to participate nationwide.
	All RT-PCR tests are conducted at the DTU test center and all retrospectively testing
	of samples by antigen tests is conducted in collaboration between DCM Hvidovre,
	Rigshospitalet and SSI.
Eligibility criteria	Inclusion criteria. Age 18 years or over, has the capacity to give informed, written
	consent and be able to cooperate to the additional testing.
	Exclusion criteria. Individuals not fulfilling the inclusion criteria or declining
	additional pharyngeal swabbing or saliva swabs.
Interventions	200 consecutive individuals are tested for SARS-CoV-2 by RT-PCR and antigen test.
	When RT-PCR results are available, additional individuals who has tested positive for
	SARS-CoV-2 (within 24 hours of positive test result to contact) are invited to
	participate in the study. SARS-CoV-2 positive individuals are retested until 200 RT-
	PCR positive individuals and 200 RT-PCR negative individuals have been included for
	each antigen test.
	Testing is done with three oropharyngeal swabs at a time in a tree point swab
	procedure. The three swabs are held together and rotated at both tonsils and at the
	back of the oro-pharynx. Additional nasal swabs, saliva swabs or breath test will be
	collected for additional antigen and RT-PCR testing.
	The consecutive 200 individuals are tested locally by RT-PCR and the residual
	volume in NEST-buffer is sent to the DTU test center to ensure that all individuals
	are tested in the same RT-PCR setup. Saliva swabs are when relevant processes
	according to the manufactures procedure locally and the samples are sent to the
	DTU test center for RT-PCR. Additional oropharyngeal swabs, nasal swabs, saliva
	collection, self-test and breath tests are used for antigen testing according to the
	manufacturer's instructions locally at the test center. Positive patients that are
	retested, are tested at home / bed-side by an range of antigen tests and one
	oropharyngeal swab is sent to DTU test center for RT-PCR together with samples
	from other anatomical test locations when relevant. For self-test tested individuals
	will send a picture and their interpretation of the test to the test-coordinator.
	The DTU test center will test for two targets in the Nucleocapsid protein gene (N-
	gene) of SARS-CoV-2 and for the RNase P gene (RP-gene) from humans to as process
	control and confirmation of the presence of human DNA in the sample.
	Excess material from negative patients will be discharged after testing. Excess
	material from previous positive patients will be discharged. Sample material from

	prospective positive individuals will be treated according to normal practice at the
	local DCM.
	For the retrospective study arm, stored excess material from 200 previously positive
	and 100 negative SARS-CoV-2 samples stored at -80 °C is defrosted on ice and
	checked by RT-PCR to ensure the Cq value. Selected samples are defrosted again on
	ice and aliquoted into 250 μL volume and stored at -80 °C until use. For each test
	one aliquot of each sample is defrosted and 200 µL sample in UTM is tested
	according to the manufacturer's instruction by laboratory trained personnel in
	collaboration between DCM Hvidovre, RH and SSI. One aliquot is used for each test
	and excess material is discharged. One aliquot is retested by RT-PCR after thawing to
	verify the Cq of the sample.
Outcomes	Primary outcome: Performance of each antigen in relation to the RT-PCR test result.
	Secondary outcomes: Performance of each antigen test in relation to the cycle of
	quantification Cq by RT-PCR with and without normalization towards human DNA.
	The fraction of consecutive samples negative for human DNA by RT-PCR.
	Agreement between oropharyngeal swabs and tests from other anatomical test
	locations by RT-PCR.
	Analytical sensitivity and specificity of each antigen test on retrospectively collected
	SARS-CoV-2 positive and negative samples. SARS-CoV-2 positive samples are
	stratified into subgroups according to Cq by RT-PCR.
Participant	Either included when referred to SARS-CoV-2 testing and agrees to participate in the
timeline	testing or being invited as in-patient, by phone or electronically and agrees to
	retesting after a positive SARS-CoV-2 RT-PCR test. Invited in- or out-patients positive
	for SARS-CoV-2 are retested with their consent again as soon as possible after first
	positive RT-PCR test by an outpatient screening team, who visits and samples each
	patient at home or for in-patients by trained hospital personnel.
Sample size	Prospective study arm. 200 SARS-CoV-2 RT-PCR positive and 200 SARS-CoV-2 RT-PCR
Sample size	negative patients included for each antigen test.
	Retrospective study arm. 200 SARS-CoV-2 RT-PCR positive and 100 SARS-CoV-2 RT-
Da amaitma anat	PCR negative samples retested for each antigen test.
Recruitment	Individuals with suspected SARS-CoV-2 infection referred to a test center are asked
	for participation in the study and given the information for participants. Those
	agreeing for participation in the study sign a consent form. Individuals who test
	positive for SARS-CoV-2 are invited to participate in the study by either 1) personal
	contact with hospital personnel for in-patients, 2) by phone or 3) by electronic
	invitation, which is sent together with the information for participants as a mail in e-
	boks. The mail is sent to the individual by the laboratory or test-center overseeing
	the local testing as an invitation for participation. Individuals are asked to contact the
	local laboratory either by phone or mail, depending on the local setup and to provide
	a phone number to provide further information and planning of additional testing if
	relevant. When retested at the hospital or by the out-patient testing team a signed
	consent form for participation will be collected.

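### The prospective stopping rule ties retesting of known positives to the RT-PCR-negative quota, so a known case with a negative retest can enter the specificity estimate

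*Protocol*

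**What the plan says.** The Interventions entry of the protocol (Methods: Participants, interventions, and outcomes) describes two streams for the prospective arm. The first is a fixed series: "200 consecutive individuals are tested for SARS-CoV-2 by RT-PCR and antigen test". The second consists of additional people with a positive result already: "SARS-CoV-2 (within 24 hours of positive test result to contact) are invited to" participate.

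The next sentence gives the accrual rule. Its subject is the second stream, "SARS-CoV-2 positive individuals are retested until 200 RT", and its end condition covers both result groups: "PCR positive individuals and 200 RT-PCR negative individuals have been included for" each antigen test.

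A retest produces its own reference result, because one "oropharyngeal swab is sent to DTU test center for RT-PCR together with samples" from other sites where relevant. The Sample size entry repeats 200 positives and 200 negatives per antigen test and does not say which stream supplies the negatives.

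Further on, the Interventions entry treats the two groups separately when it deals with leftover material: "Excess material from negative patients will be discharged after testing", and likewise excess "material from previous positive patients will be discharged". That text concerns disposal, not accrual.

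**The concern.** As written, retesting people known to be infected is the activity that continues until the negative quota is filled. A known case whose retest swab is negative would then count among the 200 negatives.

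Specificity is part of the primary outcome as the Statistical methods entry sets it out. The study is placed in test centers screening out-patients and staff, as well as among hospitalized positives, and its stated purpose is accuracy in real-life use. Recently confirmed cases with a negative retest differ from screened people who do not have the infection. If they are antigen-positive more often than other negatives, the specificity reported for a test would be lower than a screening program would see. How far depends on how many known cases enter the negatives, and the protocol leaves that uncontrolled.

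**Working it through.** **Step 1. Follow a retest-negative known case through the text.** The retest has a new RT-PCR swab (Interventions). It gets a new sample identifier that pairs this RT-PCR with the antigen tests done at that visit (Data management). Performance is judged against RT-PCR on the oropharyngeal swab, with no separate rule for known cases (Statistical methods). The Sample size entry does not restrict where negatives come from. No entry keeps such a pair out of the specificity denominator.

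**Step 2. Can the consecutive series alone meet the target?** The protocol gives no power or precision basis for the 200 and 200, so there is no figure to reproduce. Inputs:

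- From the protocol: 200 consecutive people and a target of 200 negatives.
- Assumed: prevalence p = 1%, 2% or 5%; specificity in other negatives s = 99.5%; antigen positivity in retest-negative known cases a = 5% or 10%.

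Formulas:

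- Expected negatives = 200(1 - p); shortfall = 200p; chance that all 200 are negative = (1 - p)^200.
- Specificity when known cases fill only the shortfall = 1 - [(1 - p) × 0.005 + p × a].
- Loss = p(a - 0.005); extra expected false positives per 200 negatives = 200p(a - 0.005).

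| p | Expected negatives | Shortfall | Chance all 200 negative | Specificity, a = 5% to 10% | Loss, points | Extra false positives |
|---|---|---|---|---|---|---|
| 1% | 198 | 2 | 13% | 99.455% to 99.405% | 0.045-0.095 | 0.09-0.19 |
| 2% | 196 | 4 | 1.8% | 99.410% to 99.310% | 0.09-0.19 | 0.18-0.38 |
| 5% | 190 | 10 | 0.004% | 99.275% to 99.025% | 0.225-0.475 | 0.45-0.95 |

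For scale, the standard error at n = 200 is sqrt(0.995 × 0.005 / 200) = 0.50 points. The largest loss in the table is 0.475 / 0.50, about 0.95 standard errors. The smallest is about 0.09.

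**Step 3. Retest-negatives also arise without a shortfall.** Filling the positive quota needs 200 - 200p positive retests. This produces (200 - 200p) × r/(1 - r) negative ones, where r is the assumed share of retests that are negative. At p = 1%, r = 2%, 5% or 10% gives 198 × r/(1 - r) = 4.0, 10.4 or 22.0. Their classification therefore has to be settled in any case.

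**Step 4. How far the answer depends on the assumptions.** If a equals 1 - s there is no loss. If a = 0 specificity rises slightly, by p × 0.005 = 0.005 to 0.025 points. Harsher inputs give more: with s = 99%, 10 known cases among the 200 negatives and half of them antigen-positive, specificity is (190 × 0.99 + 10 × 0.5) / 200 = 96.55%. That is a loss of 2.45 points, against a 95% half-width of 1.96 × sqrt(0.99 × 0.01 / 200) = 1.38 points. None of these inputs is in the protocol.

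**The case against.** The strongest reply is that the sentence is only loosely worded. It may mark when accrual for an antigen test is complete, without saying that retests supply both groups. The order of the text (200 consecutive people, then additional positives, then the totals) fits that, and so does the separate naming of the two groups in the disposal text. This is probably the intent. It is not stated, however, and a fixed 200 cannot deliver it once one person is positive.

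A reader might infer that retested cases are the only possible source for the shortfall. That holds only within the Interventions entry. The Participant timeline and Recruitment entries describe enrolment of referred people without stating a cap, though also without saying that it continues past 200.

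A reader might also infer that such pairs are wrongly classified. They are not: against the same-visit RT-PCR, an antigen-positive, RT-PCR-negative pair is a discordance whoever gave the sample. What remains is case mix, which matters if specificity is to describe screened people.

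It is fair that the analysis set and the route flag could be defined in an SAP, which is not shown. The rule for who is retested and when accrual stops is a protocol rule, and it is in the current text. It is also fair that contact within 24 hours and prompt retesting should keep retest-negatives few.

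**Conclusion.** The point stands as a minor one. The accrual rule, followed as written, allows recently confirmed cases into the negative group used for specificity, against the likely intent. Under the assumptions of the table, filling only the shortfall costs about 0.05-0.5 points, at most about one standard error. Other assumed inputs give anything from no loss to a loss beyond the confidence-interval half-width, so neither size nor direction is established.

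Two stronger conclusions are not supported. A reader might infer that specificity will be biased downward; that needs retest-negative known cases to be antigen-positive more often than other negatives, and the protocol gives no figure for it. A reader might also infer from "The provider delivers 800 antigen-tests free-of-charge" that supply would make the negative quota unreachable; the protocol neither allocates those tests between the arms nor calls 800 a ceiling.

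**What to change.** - Reword the stopping sentence under Interventions so that retesting of known positives continues until 200 RT-PCR positives are included, with no reference to negatives.
- Restate the negative target there and under Sample size as the RT-PCR negatives among the 200 consecutive individuals.
- Compute prospective specificity on those consecutive negatives.
- Record recruitment route for every participant, and report known cases with a negative retest as a separate group.

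The cost is a change of wording in two entries and one data flag; retests already receive a new identifier. The negative group becomes slightly smaller than 200: 190-198 expected at an assumed prevalence of 5% to 1%. Precision hardly changes: at 99.5% specificity the standard error is sqrt(0.995 × 0.005 / 190) = 0.51 points at n = 190 and 0.50 at n = 198, against 0.50 at n = 200. The 200-positive target is unaffected.

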### Methods: Data collection, management, and analysis

Data collection	RT-PCR result is reported with cycle of quantification Cq for positive tests together
methods	with the Cq for human DNA in the sample.
	Antigen tests are reported according to the manufactor's instruction and divided
	into positive, negative, inconclusive or invalid tests. Inconclusive and invalid tests

	are handled according to the manufactor's instruction. Each antigen test is
	photographed to document the result.
	In the retrospective study arm all antigen tests are tested with stored excess
	material with seeking 50 samples with Cq 20 to 25, 50 samples with Cq 25 to 30, 50
	samples with Cq 30-35 and 50 samples with Cq >35. The 100 negative samples are
	pooled negative samples that are retested by RT-PCR again prior to use.
Data	Written consent for participation and collection of data in the study will be collected
management	at the test center and each consent is marked with the local sample identifier
	number. For consecutive samples each antigen test and the sample for RT-PCR at
	the DTU test center will be marked with the local sample identifier number and data
	will be paired according to this sample identification number. Individuals positive for
	SARS-CoV-2 will be invited in person, by phone or electronically for additional
	testing and individuals who agrees to additional testing, except in-patients will be
	contacted using their self-reported contact information's. The number of individuals
	contacted and rejecting participation will be registered, without additional
	information. At each retest a new sample identifier number will be pair with the
	swab(s) for RT-PCR testing at the DTU test center and the antigen tests conducted
	bedside by trained hospital personnel or outpatient team. Data including photo
	documentation of antigen test results will be send to the steering group and stored
	in a secure regional file archive.
Statistical	Prospective arm: Performance of each antigen test will be reported as sensitivity,
methods	specificity, positive predictive value (PPV) and negative predictive value (NPV)
	compared to oropharyngeal swabs evaluated by RT-PCR. Clinical performance of
	antigen tests will be further evaluated in respect to strong (Cq <25), intermediate
	(Cq 25-35) and weak (Cq >35) RT-PCR tests and in respect to samples with low SARS-
	CoV-2 RNA to human DNA ratio, equal SARS-CoV-2 RNA to human DNA ratio and
	high SARS-CoV-2 RNA to human DNA ratio.

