	Among consecutive collected prospective samples the fraction of samples negative
	for human DNA by RT-PCR will be reported.
	Retrospective study arm: Determination of analytical sensitivity, specificity stratified
	into four groups by PCR (Cq 20-25, Cq 25-30, Cq 30-35 and Cq >35).
	Comparison of sensitivity and specificity between antigen test will be done using
	McNemar chi-squared test. Comparison of PPV and NPPV between antigen test will
	be done by bootstrap test.
	95 % Confidence intervals for sensitivity, specificity, positive predictive value and
	negative predictive value are calculated as bootstrap confidence intervals.

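### The two three-group splits describe antigen performance by raw Cq and by RNA-to-human-DNA ratio, but as planned they do not show what normalisation adds

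*Protocol*

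**What the plan says.** In the protocol's Methods: Participants, interventions, and outcomes, the first secondary outcome is the performance of each antigen test in relation to "quantification Cq by RT-PCR with and without normalization towards human DNA". The human target is the RNase P gene, measured as process control and as "control and confirmation of the presence of human DNA in the sample".

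In Methods: Data collection, management, and analysis, the Statistical methods entry for the prospective arm names two groupings. The first is raw Cq: below 25, 25 to 35, and above 35. The second is the viral-RNA-to-human-DNA ratio: low, equal and high. The text runs "Cq 25-35) and weak (Cq >35) RT-PCR tests and in respect to samples with low SARS" and continues "CoV-2 RNA to human DNA ratio, equal SARS-CoV-2 RNA to human DNA ratio and" a high-ratio group. No cross-classification of the two is described, and neither is a model containing both Cq values.

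The comparative tests that are named concern different antigen tests ("Comparison of sensitivity and specificity between antigen test will be done using" the McNemar test, with a bootstrap test for predictive values). None sets raw Cq against normalised Cq.

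The data for a joint analysis will exist. Data collection methods says that the viral Cq of positive tests is reported together "with the Cq for human DNA in the sample". The planned number is 200 RT-PCR positives per antigen test.

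**The concern.** On the Cq scale the log ratio is the human Cq minus the viral Cq. Viral Cq is therefore inside the ratio, and antigen sensitivity depends strongly on viral Cq. Grouping by ratio sorts people largely by viral Cq, so a steep gradient appears whether or not human DNA matters. Moving the group limits does not remove it.

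What is at stake is the reading of the results. For every antigen test the ratio split would look like a clear effect of normalised viral load. A reader who wants to know whether normalising changes the picture would find two gradients on differently composed groups and no quantity that links them.

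**Working it through.** The protocol states no figure for this outcome, so there is none to reproduce. The only input from the document is 200 positives per antigen test. All Cq distributions, slopes and ratio limits below are assumptions.

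**Step 1: how much of the ratio is viral Cq.** If the two Cq values are independent, the correlation of viral Cq (N) with the normalised value (N − R) is SD_N / √(SD_N² + SD_R²). With SD_N 5 and SD_R 2.5 this is 5 / √(25 + 6.25) = 5 / 5.59 = 0.89. With 5.5 and 3 it is 5.5 / √(30.25 + 9) = 0.88. Over the simulated settings, including a correlation of 0.3 between N and R, it ranged from 0.59 to 0.98.

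**Step 2: what the two splits would show.** Assume N has mean 27 and SD 5, and RNase P Cq R has mean 26 and SD 2.5. The logit of a positive antigen result is −0.6(N − 29) + b(R − 26), and the ratio limits are R − N = ±2. Here b = 0 means that human DNA is irrelevant, and b = 0.6 means that only the normalised value matters.

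| Truth | Raw Cq <25 / 25–35 / >35 | Ratio low / equal / high |
|---|---|---|
| b = 0 | 97 / 50 / 1% | 33 / 77 / 96% |
| b = 0.6 | 95 / 49 / 3% | 24 / 84 / 99% |

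The ratio groups shift by 9, 7 and 3 points between opposite truths. R − N has mean −1 and SD 5.59, so the low, equal and high groups hold about 43%, 28% and 30% of 200, or 86, 55 and 59 people. The standard errors at b = 0 are:

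- low: √(0.33 × 0.67 / 86) = 5.1 points
- equal: √(0.77 × 0.23 / 55) = 5.7 points
- high: √(0.96 × 0.04 / 59) = 2.6 points

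The shifts are thus about 1.8, 1.2 and 1.2 standard errors of a single group. The gradient itself is 96 − 33 = 63 points with no human-DNA effect at all.

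**Step 3: does this depend on the assumptions?** A second set-up used ratio tertiles, mid-point 29 and b = 0. It varied mean viral Cq 24–30, its SD 4–7, human Cq SD 1–4 and slope 0.25–0.8. The high-minus-low ratio gradient ran from 26 to 95 points. Its size depends on the assumptions, but it was present in every case.

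Two different truths can also look alike. With viral Cq mean 27, SD 5.5 and slope 0.5:

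| Truth | Raw Cq groups | Ratio tertiles, high / mid / low |
|---|---|---|
| b = 0, human Cq SD 1 | 0.961 / 0.482 / 0.020 | 0.962 / 0.704 / 0.194 |
| b = 0.25, human Cq SD 3 | 0.952 / 0.482 / 0.026 | 0.961 / 0.698 / 0.192 |

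These differ by at most 1 point. The 95% half-width with 67 per tertile, 1.96√(p(1 − p)/67), is 5 points at p = 0.95 and 12 points at p = 0.5.

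**Step 4: what a joint model gives.** Logistic regression on both continuous Cq values, 200 positives, two-sided 5%. Half normalisation means that b is half the viral slope. Repeat runs are shown as ranges.

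| Viral slope, RNase P SD | No effect | Half | Full |
|---|---|---|---|
| 0.6, 2.5 | 3–5% | 92–93% | about 100% |
| 0.5, 3 | 5.8% | 93% | 100% |
| 0.5, 2 | 4.3% | 64% | 99% |
| 0.4, 2 | – | 50–54% | – |
| 0.25, 2 | – | 31–33% | – |

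For a small effect (b = 0.1, slope 0.5) power is only 14% at SD 2 and 30% at SD 3.

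**The case against.** A reader might infer that the secondary outcome goes unanswered. The document does not support that. The outcome is descriptive: it asks for performance by Cq on each scale, the splits give exactly that, and no test of whether normalisation matters is promised.

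A reader might also infer that the planned groupings could never reveal anything about normalisation, or that the continuous values are thrown away. Neither follows. Both Cq values are recorded, and the wording does not exclude further analysis. With matched tertiles on both scales, under the Step 2 assumptions, the ratio gradient is steeper than the raw one in about 1% of runs if human DNA is irrelevant and 99% under full normalisation. Keeping the Cq limit of 25 and matching the high-ratio group to it in size gives about 4% against 86%, and the latter falls to 71% at RNase P SD 2. If all scenario parameters were known, the three ratio-group sensitivities would classify the two truths correctly in 91% of runs. So the data hold a signal. But the protocol plans no such comparison, its raw Cq limits are fixed without matching ratio limits, and a reader would not know those parameters.

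An unseen SAP could add a joint analysis. Missing detail is not the complaint here: the protocol names the evaluation, and the one it names leaves the effect of normalising unseparated from viral Cq.

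Three practical limits stand and shape the fix: some samples may have no detectable human DNA, the laboratory measures two N-gene targets, and some antigen tests use other swabs or sites than the PCR swab.

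**Conclusion.** The point holds as an improvement to the analysis of a secondary outcome. The two splits describe performance on each scale. Because the ratio contains viral Cq, the ratio split shows a steep gradient even when human DNA is uninformative, so the splits as planned do not show what normalisation adds. The direction follows from how the ratio is built and from sensitivity falling with viral Cq. The size (63 points in one base case, 26 to 95 over a grid) rests on Cq distributions and slopes that the protocol does not give. The primary outcome, the sample size and the participants are unaffected, and the priority is low.

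**What to change.** Keep both splits, labelled as descriptive. Add to Statistical methods, for each antigen test among RT-PCR positives:

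- A logistic regression of the antigen result on continuous N-gene Cq and continuous RNase P Cq. State in advance which N-gene target enters, or use the mean of the two.
- As main result, the RNase P coefficient with its 95% CI, and the likelihood-ratio test as support. A coefficient near zero points to raw Cq; one equal and opposite to the N-gene coefficient points to full normalisation. The difference in AUC between raw and normalised Cq is optional.
- Separate reporting of samples with no detectable RNase P, which have no continuous Cq to enter.
- Interpretation limited to antigen tests on oropharyngeal swabs taken together with the PCR swab. RNase P in that swab does not measure cell content in nasal, saliva or breath samples.
- A statement that a non-significant coefficient does not prove that raw Cq suffices. Power at half normalisation ranges from about 30% to above 90% over the slopes and RNase P spreads tried.

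The cost is a few sentences and a little more analysis of data already collected, with no extra samples or participants. The drawback is limited power for small effects.

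### The protocol neither records nor accounts for a prior antigen test among recruited RT-PCR positives, so sensitivity may be biased upward by an amount that cannot be checked

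*Protocol*

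**What the plan says.** All references are to the Protocol, Methods: Participants, interventions, and outcomes, unless stated.

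- **Interventions.** After 200 consecutive people have been tested, the positives are topped up: "When RT-PCR results are available, additional individuals who has tested positive for" SARS-CoV-2 are invited, and this continues until each antigen test has 200 RT-PCR positives and 200 RT-PCR negatives.
- **Participant timeline.** The invited group agrees to "retesting after a positive SARS-CoV-2 RT-PCR test. Invited in- or out-patients positive" are then retested as soon as possible.
- **Recruitment.** People who test "positive for SARS-CoV-2 are invited to participate in the study by either 1) personal" contact, phone or electronic mail. The test is not named here. The consecutive group is described separately: "Individuals with suspected SARS-CoV-2 infection referred to a test center are asked" to take part.
- **Eligibility criteria.** Inclusion rests on adult age, capacity to consent and ability to cooperate. Exclusion covers failing these or declining the extra swabs. Neither mentions an earlier antigen test or the reason for the RT-PCR.
- **Data management and Statistical methods** (Methods: Data collection, management, and analysis). No data item for prior antigen testing is listed. Sensitivity against oropharyngeal RT-PCR is reported overall and by Cq band, but not by how the person came to be tested.
- **Background and rationale.** "Multiple antigen tests targeting SARS-CoV-2 are being marketed commercially", so earlier use by a participant is possible.

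**The concern.** Sensitivity is the share of RT-PCR positives that a kit detects. A person sent for RT-PCR because of a positive antigen result has already passed a test of the kind under evaluation, and infections that the first test missed do not enter by that route. If those missed infections do not reach RT-PCR by another route either, the denominator loses cases that the study kits would tend to miss. Measured sensitivity then rises, and the planned bootstrap intervals would not show it. Kits that behave most like the earlier test would gain most, which also bears on the planned McNemar comparisons.

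This cannot be left wholly to an analysis plan. If prior antigen testing is not collected at enrolment, no later analysis can separate these people.

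**Working it through.** **What is given.** The protocol states 200 RT-PCR positives per kit, without an expected sensitivity or precision target, so there is no planning figure to reproduce. It also gives no prevalence, no share of antigen-prompted positives and no correlation between antigen tests. These are assumptions below.

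**Step 1: where the positives come from.** At an assumed prevalence of 1% to 10%, the consecutive 200 yield 200 × 0.01 = 2 to 200 × 0.10 = 20 positives. The other 180 to 198 must then be invited as known positives, so the concern falls mainly on that group.

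**Step 2: size if the route is open and antigen-negatives do not reach RT-PCR.** Let Se be the true sensitivity of the study kit and of the earlier test (taken as equal), φ their correlation among RT-PCR positives, and f the share of positives that were antigen-prompted.

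- Sensitivity among prior antigen-positives: c = Se + φ × √[Se(1−Se)(1−Se)/Se] = Se + φ(1−Se).
- Observed sensitivity: (1−f)Se + f·c, so bias = f·φ·(1−Se).
- At Se = 0.60, c = 0.72 for φ = 0.3 and 0.88 for φ = 0.7.

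| f | Observed sensitivity (true 0.60) | Bias, points |
|---|---|---|
| 0.10 | 0.612 to 0.628 | +1.2 to +2.8 |
| 0.25 | 0.63 to 0.67 | +3 to +7 |
| 0.50 | 0.66 to 0.74 | +6 to +14 |

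At f = 0.50 the bias is +7.5 to +17.5 points for Se = 0.50, and +3 to +7 for Se = 0.80. With f = 0 or φ = 0 it is zero.

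**Step 3: random error for comparison.** The 95% half-width at n = 200 is 1.96 × √(0.60 × 0.40/200) = 0.068, and 0.055 at Se = 0.80.

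**Step 4: what happens if antigen-negatives also reach RT-PCR.** Suppose 30% of infected people took an earlier antigen test, with Se = 0.60 and φ = 0.5. Then c = 0.80. Sensitivity among prior antigen-negatives is 0.60 − 0.5 × √(0.60 × 0.40 × 0.60/0.40) = 0.30. The groups are: no prior test 0.70, prior positive 0.30 × 0.60 = 0.18, prior negative 0.12.

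- Everyone reaches RT-PCR: 0.70 × 0.60 + 0.18 × 0.80 + 0.12 × 0.30 = 0.600. There is no bias.
- No prior negative reaches RT-PCR: (0.420 + 0.144)/0.88 = 0.641, or +4.1 points.
- Everyone reaches RT-PCR, but prior positives are excluded: (0.420 + 0.036)/0.82 = 0.556, or −4.4 points.
- No-prior-test group alone: 0.60 in all three cases.

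**Step 5: how far the Cq strata help.** Assume sensitivities of 0.95, 0.55 and 0.10 in strong, intermediate and weak samples, with a mix of 40%, 45% and 15%. Overall sensitivity is 0.380 + 0.2475 + 0.015 = 0.643. If all positives were antigen-preselected it becomes 0.776, and if half were, 0.709; the weak share falls from 15% to 2% among the preselected. If selection acts only through these bands, the stratum figures stay right while the pooled figure does not.

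**The case against.** A reader might infer from Recruitment that people are enrolled on an antigen result alone. The documents do not support this. Interventions ties the invitation to available RT-PCR results, and Participant timeline names a positive RT-PCR. The unnamed test in Recruitment is a wording gap; the route that stays open is an RT-PCR taken after a positive antigen test.

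A reader might also infer that every kit will look too sensitive. That does not follow, for four reasons, all of which stand:

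- No section says that RT-PCR was used to confirm antigen positives. The sources described are test centres screening out-patients and hospital staff, plus in-patients, and Research ethics approval treats antigen testing in health care as an open question. The share could be near zero.
- Step 4 shows no bias when antigen-negative infections reach RT-PCR equally.
- The interval between first positive and retest could lower sensitivity, so the net direction in the whole positive group is undetermined.
- Larger figures need extreme inputs. Pairing a true sensitivity of 0.55 with 0.95 among prior positives gives +20 points at a 50% share, but requires φ = (0.95 − 0.55)/0.45 = 0.89.

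The strata by Cq, and the retrospective arm with its target of 50 positives in each of four Cq bands, are real safeguards. They are partial: neither corrects the pooled prospective sensitivity, and the intermediate band, Cq 25 to 35, is wide enough for selection to act within it.

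**Conclusion.** The gap is real. The protocol relies on known positives to fill its target and has no means of telling which were pre-selected by an antigen test. Upward bias needs two conditions that the documents neither confirm nor rule out: a material antigen-prompted share, and lower access to RT-PCR for antigen-negative infections. Where both hold, shares of 25% to 50% give a bias that can match or exceed the sampling error at n = 200, on the assumed sensitivity and correlations. At a 10% share it stays well inside the sampling error. The finding is therefore that the bias is possible and cannot be checked, not that inflation is demonstrated.

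**What to change.** 1. In Recruitment, name RT-PCR as the test whose positive result triggers the invitation, to agree with Interventions and Participant timeline.
2. At consent, ask every prospective participant, consecutive and invited, whether an antigen test was taken earlier in this episode and with what result: none, negative or positive. List this under Data collection methods.
3. In Statistical methods, report sensitivity overall and, as a pre-specified analysis, among RT-PCR positives with no prior antigen test. Show the prior-positive and prior-negative groups separately.
4. Do not exclude only the prior antigen-positives. That keeps the prior antigen-negatives and can push sensitivity down (−4.4 points in the illustration).

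The no-prior-test analysis removes selection by an earlier antigen result in either direction. It still assumes that people who took no antigen test are otherwise comparable, so both figures should be shown.

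The cost is one question and wider intervals in the subset. At a sensitivity of 0.60, the half-width is 1.96 × √(0.24/150) = 7.8 points with 150 positives and 1.96 × √(0.24/100) = 9.6 points with 100, against 6.8 with 200. If almost nobody reports a prior test, little precision is lost and the study can show that this bias is negligible.
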